9.2.1 Treatment Assignment Procedures

Details regarding how participants will randomly be assigned to one of the two study conditions (PPMI vs. EUC) are described above (see Section 5. “Study Conditions”, Section 6.2.2 “Enrollment, Baseline, and Randomization”, and Section 6.2.3 “Blinding”).

Randomization will be stratified by gender (biologically assigned male versus biologically assigned female at birth), past year use of heroin (yes/no), and veteran status (community/veteran). There is no sample size goal for each stratum, although strata assignment

and condition assignment will be monitored throughout the study to ensure an imbalance does not occur that could impact the ability to report on main study outcomes. Data on adherence to the intervention condition's protocol will be collected monthly by research staff and reviewed monthly by the PI/Project Managers. Adherence of participants will be evaluated by the Project Managers. If adherence falls below the expected rate, which might inhibit the ability of the study to test its primary hypotheses, the Project Managers will suggest a conference call for study investigators to discuss methods for improving adherence.

9.3 Definition of Populations

For this study, analysis will use an intent-to-treat (ITT) framework, where participants are classified by the condition they were randomized to, regardless of what they received. Cox Proportional Hazards regression models will be used to test the association between group assignment and time to dropping out of buprenorphine treatment. We will test whether the assumptions for this modeling technique are met, and if they are not, consider variable transformations or alternative modeling strategies (e.g., generalized linear models).

While primary analyses will use the ITT framework, we will further examine treatment effects by conducting a per-protocol analysis. As stated earlier (see Section 5.4 "Adherence Assessment"), participants will be considered to be "per-protocol" if they complete at least 4 sessions of the PPMI condition, or 1 session of the EUC condition. This cutoff equates to receiving 50% of the proposed material which will be sufficient to consider the intervention condition being received by the participant. Prior to conducting this analysis, we will verify the assumption that this cut-off represents a level of treatment compliance for participants (as intended by the study design) by comparing the associations of patient characteristics with the likelihood of attending six or more sessions. If this assumption is not met, we will consider alternative methods for comparing condition groups, such as complier average causal effect models, which use latent variable/training data methods to assign compliance levels for EUC group participants.

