In order to keep non-specific factors relatively consistent across conditions, PPMI and EUC will be delivered with the assistance of a manual and over the same time interval. Both conditions will be delivered by masters-level therapists trained specifically on the study treatment manual content. In order to effectively and efficiently deliver both conditions, the same study therapists will be trained to deliver both conditions. The PPMI conditions will involve 8 individual therapy sessions meant to be delivered via phone or video chat approximately 2 times per week over a total of 4 - 6 weeks. The EUC condition will involve two brief, educational sessions delivered via phone or video chat approximately once every 2 weeks (biweekly) over a total of 4 – 6 weeks. Participants will have a total of 6 weeks post study enrollment to complete all study sessions (8 total for PPMI condition, 2 total for EUC condition). Participants will not be allowed to complete any condition sessions following that 6-week deadline in order to ensure the maximum completion of the 1-month follow-up study visit.

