5.4 Adherence Assessment

For this study, adherence to the study intervention condition (PPMI) will be defined as participation in at least 50% of the condition sessions. This would equate to participating in at least 4 of the 8 study sessions. The PPMI condition is designed to be progressive in nature, with each

session building on materials learned or discussed during previous sessions. Because of this, receiving at least 4 sessions of material in the PPMI condition related to chronic pain management and buprenorphine adherence/retention, will be considered an adequate dose. Likewise, adherence to the study control condition (EUC) will also be defined as participation in at least 50% of the condition sessions, or 1 of 2 study sessions. Due to the nature of the study (a behavioral therapy intervention study), participants will not be required to attend study sessions and will not be compensated for their involvement in the individual sessions. Study therapists and research staff will discuss the benefits of remaining engaged in the study treatment during the initial study meeting, however participants will be free to discontinue the study sessions at any time. Study therapists will make reasonable attempts to contact the participant should they disengage from the sessions. Participants will only be allowed to complete study sessions up to 6 weeks post enrollment. This cutoff was determined to allow for adequate time for the participant to complete the 1-month follow-up assessment. Participants will be eligible to participate in all follow-up assessments regardless of study session participation.

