Once generated, documents that include the randomization sequence will be password protected to avoid inadvertent access by research staff involved in the enrollment process. Research staff will contact the project managers to randomize all participants using the randomization sequence provided by the biostatistician. The randomization process will be overseen by the project managers who will be notifying the research therapists of assigned

condition for specific participants at the completion of all baseline assessments. Randomization will occur once the baseline enrollment assessments are complete, which will take place no later than 60 days following the completion of the eligibility screening survey. Initiation of the study treatment condition (either PPMI or EUC) will occur immediately following randomization, when possible. Study sessions delivered via telephone or video chat should take place within one week of study enrollment and randomization for those in the PPMI condition and within two weeks of study enrollment and randomization for those in the EUC condition in order to provide enough time for all sessions to be completed within the 4-6-week treatment window.

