9.2 Sample Size and Randomization

Sample size estimates were guided by our prior work on psychosocial interventions for pain during addiction treatment and prior trials that used MAT retention as an outcome and calculated using Stata. In studies of buprenorphine programs, retention varies widely but generally is around 50% in studies with at least 3-months of follow-up and robust sampling.²⁶ For a time-to-event analysis we assumed an event rate of 50% in EUC, where the event is dropping out of treatment, and based calculations on a two-sided $\alpha=0.05$. A hazard ratio of 0.5 (i.e., PPMI less likely to drop out of treatment) would achieve >85% power with a sample size of 200, or 100 per group. Given that we will be able to infer treatment retention even for participants who drop out of the study, our primary outcome analysis was based around our complete sample size of 200.

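### The per-protocol set in 9.3 is defined by sessions attended after randomisation, reached later in PPMI than in EUC, so a Cox model run from randomisation can make an ineffective PPMI look protective

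*Combined protocol and SAP*

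**What the plan says.** Section 9.3 makes ITT primary and names Cox regression for time to leaving buprenorphine treatment. It then adds a per-protocol analysis to look further at treatment effects. Participants qualify if "they complete at least 4 sessions of the PPMI condition, or 1 session of the EUC condition". Section 5.4 gives the same thresholds; for EUC, adherence "will also be defined as participation in at least 50% of the condition sessions, or 1 of 2 study sessions".

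The timing of sessions is set elsewhere:
- Section 5.1 plans about two PPMI sessions a week over 4-6 weeks, and two EUC calls of 5-10 minutes each. "Participants will have a total of 6 weeks post study enrollment to complete all study sessions".
- Section 6.2.2 asks for sessions to start "within one week of study enrollment and randomization for those in the PPMI condition and within two weeks of study enrollment and randomization" for EUC. It also counts a participant as enrolled only once randomised.
- Section 6.2.3 measures the primary outcome over the three months after enrolment, and 9.5.1 defines the event as a gap of seven or more days without buprenorphine.

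Section 9.3 gives no separate model, time zero, landmark, delayed entry or weighting for the per-protocol analysis. Its one safeguard is to examine how patient characteristics relate to attending six or more sessions. Complier average causal effect models are to be considered if that check fails.

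**The concern.** Entry to the per-protocol set and the outcome overlap in time. Take a person who stops buprenorphine in week 2 and also stops answering the therapist. In PPMI that person usually falls short of four sessions and is excluded, event and all. In EUC the same person needs only one short call and is usually kept, with the event counted. PPMI participants in the set then carry a longer stretch in which they could not have had the event and still qualified.

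The six-session check cannot detect this. Six is not the entry threshold, EUC has only two sessions, and the check does not look at when drop-out occurred. The problem would also remain if four-versus-one were used consistently throughout.

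At stake is the reading of a null primary result: a per-protocol analysis tilted towards PPMI could follow it and be taken as evidence that the intervention works when it is received.

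**Working it through.** **The plan's own figure.** Section 9.2 says "we assumed an event rate of 50% in EUC, where the event is dropping out of treatment", and that an HR of 0.5 "would achieve >85% power with a sample size of 200, or 100 per group" (two-sided 0.05).
- PPMI event rate: 1 − 0.5^0.5 = 29.3%.
- Expected events: 100 × 0.50 + 100 × 0.293 = 79.3.
- Schoenfeld power: Φ(√(79.3/4) × ln 2 − 1.96) = Φ(1.126) = 87%.

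The stated power is reproduced. It concerns the ITT comparison, where "our primary outcome analysis was based around our complete sample size of 200". The plan gives no figure for the per-protocol analysis.

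**When the qualifying session falls.** Space eight sessions evenly, starting on day 0 or 7 and ending on day 28 or 42. Session 4 is at start + (3/7) × (end − start):
- ending day 28: day 12 or 16
- ending day 42: day 18 or 22

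So session 4 falls at about weeks 2-3. Dates up to day 32 are possible within the six-week limit but represent slippage. The first EUC call is due by day 14.

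**Exclusions by hand, true HR = 1.** Assume a constant hazard of ln 2/13 = 0.0533 per week, and let c be the share of buprenorphine drop-outs who stop sessions when they stop treatment. The documents do not give c. At c = 1, with mean session times of 2.5 weeks (PPMI) and 1 week (EUC):
- PPMI excluded: 1 − exp(−0.0533 × 2.5) = 12.5%.
- EUC excluded: 1 − exp(−0.0533 × 1) = 5.2% (5.1% in simulation).
- Events left by week 13: PPMI (50 − 12.5)/(100 − 12.5) = 42.9%; EUC (50 − 5.1)/(100 − 5.1) = 47.3%.

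A gap of 4.4 points in retention appears with no effect at all.

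**Simulated per-protocol Cox model from randomisation, true HR = 1.** HRs come from 400,000 per arm and rejection rates from 3,000 trials of 100 per arm. Nobody misses sessions except through drop-out.

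| PPMI session 4 / EUC session 1 | c | HR | Excluded, PPMI v EUC | Two-sided rejections (favouring PPMI) |
|---|---|---|---|---|
| Weeks 2-3 / 0-2 (schedule) | 0 | 1.00 | 0 v 0 | 4.4% (2.1%) |
| | 0.5 | 0.93 | 6.2% v 2.6% | 7.2% (5.8%) |
| | 1 | 0.84 | 12.5% v 5.1% | 12.0% (11.6%) |
| Weeks 2-6 / 0-2 (slippage) | 0.5 | 0.86 | 9.5% v 2.6% | 9.0% (8.6%) |
| | 1 | 0.71 | 19.0% v 5.2% | 31.0% (31.0%) |
| Weeks 1.5-2 / 2-4 (EUC late) | 0.5 | 1.06 | 4.5% v 7.4% | 5.3% (1.1%) |
| | 1 | 1.16 | 9.0% v 14.8% | 9.7% (0.4%) |

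The nominal rate is 5% (2.5% favouring PPMI).

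**Other settings.**
- Session 4 at days 14-21, with assumed attendance of 80% (PPMI) and 92% (EUC) among those still on treatment: HR 0.84-0.87 and 8-9.5% rejections at c = 1.
- Session 4 at days 12-22: HR 0.93 and 6% at c = 0.5; 0.85 and 11% at c = 1.
- Session 4 at days 17-32: HR about 0.75-0.77 and 16-20% at c = 1.
- Non-attendance of 30% (PPMI) and 10% (EUC), unrelated to drop-out: HR 1.01.
- The same non-attendance, but driven by a frailty shared with drop-out (SD 0.5-1.0), with slipped sessions and c = 0: HR 0.92-0.88.

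**Landmark at week 6.** Without shared frailty, HR 0.99-1.01. With it, 0.89-0.94: the immortal time is gone but the selection is not. The cost is early events: 1 − 0.5^(6/13) = 27.4% of participants, and 27.4/50 is about 55% of expected three-month events.

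**The case against.** The bias is conditional, and the documents give no figure for the condition. Section 5.3.2 keeps people who stop buprenorphine in the study, and 5.4 has therapists try to reach those who disengage. If sessions carried on regardless of drop-out, and nothing else linked the two, the HR would be 1.00. This stands, so the supportable statement is that the analysis can favour PPMI. A reader might infer that it must; the documents do not support that. They do not support the opposite either: allowing attendance to continue does not make it independent of drop-out, and section 2.1 itself argues that maladaptive reactions to pain probably affect engagement in recovery behaviour, including medication adherence.

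The direction is not guaranteed. If EUC calls run late and PPMI runs promptly, the bias reverses (HR 1.06-1.16). That requires EUC to miss its two-week target.

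The Cox model and its clock are inferred for the per-protocol analysis from the same section. This also stands; the silence is itself something to repair.

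Finally, the analysis is supplementary, 9.1 promises to separate confirmatory from exploratory work, and complier models are already named. That limits the harm. But those models are reached only through a check that would miss this problem.

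**Conclusion.** The concern holds in conditional form. The four-versus-one rule is applied after randomisation and takes longer to satisfy in PPMI on the planned schedule. With a Cox model from randomisation it can make an ineffective intervention look protective.

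Near schedule the effect is moderate: HR about 0.93 with about 6% false positives (5-7% across settings) if half of drop-outs stop attending, and 0.84-0.87 with about 8-12% if all do. Late fourth sessions (days 17-32) with full coupling give about 0.75-0.77 and 16-20%. With no coupling and no shared cause there is no bias.

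These sizes rest on a constant hazard with 50% drop-out by day 91 and on assumed attendance and coupling rates. HRs near 0.7 or below need slipped sessions with strong coupling, or added frailty, and should not be read as what the planned schedule produces. Nor should a reader infer that the primary result is in doubt: ITT simulations gave HR 0.99-1.01 with 4.4-5.5% rejections, and the stated power is reproduced. This should be corrected, but it does not threaten the primary conclusion.

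**What to change.** In 9.3:

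1. Make a randomisation-based complier average causal effect on day-91 retention the planned compliance analysis, instead of one triggered by the six-session check. With randomised arm as the instrument, it is the ITT difference in day-91 retention divided by the proportion of PPMI participants who complete at least four sessions.
2. State its assumption that one to three PPMI sessions have no effect. Section 5.1 describes fewer than four sessions as a partial dose, so the assumption is open to question, and if partial attendance helps, the complier effect is inflated. Add a sensitivity analysis that defines compliance as any PPMI session.
3. If a per-protocol Cox model is kept, label it descriptive, state its time zero, and start its clock at the day-42 session deadline among those still retained in both arms. Say that this drops about 55% of expected three-month events and does not remove selection from shared causes.

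The cost is a few lines of text, with no new data, procedures or sample size. The complier estimate has a wider interval: at an assumed 80% compliance, by about 1/0.8 = 1.25 times. In simulation under no effect its mean bias was 0.4 percentage points or less, with 5-6% false positives. That shows it is safe under the null; it does not test the partial-dose assumption.

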9.4 Interim Analyses and Stopping Rules

There are no formal interim analyses planned for this RCT. Recommendations of the Independent Monitoring Committee, IRB, the sponsor(s), or relevant local regulatory authorities, which may include review of serious, unexpected, and related AEs may result in suspension of further study conditions at a site. The study sponsor(s) retain the authority to suspend additional enrollment and study conditions for the entire study, as applicable. Findings that might trigger a safety review are the number of overall SAEs, the number of occurrences of a particular type of SAE, severe AEs/reactions, or increased frequency of events.

9.5 Outcomes

All outcome measures for this study have been selected to include high reliability, validity, and variability. Most measures have been utilized in prior research examining similar populations of interest (e.g. those with pain, those with substance use disorders, etc.). All outcomes from this study will be patient-reported outcomes (PROs), which have been widely used in clinical research trials.

9.5.1 Primary Outcome

The **primary outcome** of interest is retention on buprenorphine treatment or remaining engaged in buprenorphine treatment over a 3-month period. We hypothesize that

participants receiving the PPMI condition (intervention condition) will have higher levels of retention on buprenorphine treatment over the 3-month follow-up period when compared to participants who receive the EUC condition (control condition). For **Primary Aim 1**, retention on buprenorphine treatment will be measured using data collected from the weekly surveys and the Time Line Follow Back (TLFB). Participants will have the opportunity to complete a total of 13 surveys over the course of the first 13 weeks of the study. During these weekly surveys, participants will be asked to respond to three questions that will be used to measure treatment retention: (1) a dichotomous questions regarding treatment engagement status (“Are you still being prescribed buprenorphine as a treatment for problematic opioid use?”); (2) a question regarding number of days that the participant has taken their medication recently (“On the calendar below, please check off each day that you have taken your buprenorphine out of the past 7 days.”); and (3) a dichotomous question regarding overall buprenorphine treatment engagement since the beginning of the study (“Since you began this study on ____ {DATE} ____, has there been any time when you went for at least 7 days at a time WITHOUT taking your buprenorphine for any reason?”). Data from these weekly surveys is expected to have greater specificity than data collected during the follow-ups due to the nature of the data collection (i.e. each week versus retrospectively over several months). This weekly survey data will be utilized to guide the discussion of the TLFB during the 1- and 3-month follow-up in order to ensure all data is captured. The main outcome measure used for data analyses, therefore, will be the TLFB.

For **Secondary Aim 1**, retention on buprenorphine treatment will be measured using data collected during the Time Line Follow Back over 12-months. The Timeline Follow-Back Assessment of Substance Use (TLFB) protocol examines daily alcohol and other drug consumption over specified time intervals (e.g., 90-180 days) using monthly calendars. Several studies have demonstrated the reliability and validity of this method of assessing alcohol use using test-retest and convergent methodologies, and a recent study supports the reliability and validity for assessing drug use. Utilizing the TLFB, we will be able to collect alcohol use, drug use, and buprenorphine treatment data (including number of days the participant has taken their medication) throughout the entire follow-up period (12-months post study enrollment).

The secondary outcomes are hypothesized to meet the assumptions of continuous variables, and we will consequently use t-tests to make comparisons. If, however, the distribution of a measure is skewed, alternative modeling strategies will be used. In all analyses, we will use an intent-to-treat framework. Pain level will be measured using the Numeric Rating Scale for Pain Intensity (NRS-I), an 11-point numeric rating scale (0 = no pain, 10 = worst pain imaginable). All participants will be asked to rate their usual and worst pain over a specified time frame (e.g. past week, past 3 months, since last visit, etc.) We will take the average of these ratings as the primary measure of pain intensity. Participants will complete the NRS-I during all assessments, including the weekly surveys. Frequency of substance use will be measured using the Time Line Follow Back Interview (TLFB), a calendar-assisted structured interview that provides the participant with temporal cues to increase the accuracy of recall. Participants are asked to recall how much they drank or used any other controlled substances on each day during the specified time frame, starting with the most recent day and progressing back one day at a time. The interviewer-administered instrument has demonstrated test-retest reliability of greater than 0.86. Percent days abstinent from alcohol and drugs will be used as the primary measure of substance use at

each assessment time point (baseline enrollment assessment and 3- and 12-month follow-up assessments).

The primary outcome measure for this study is retention on buprenorphine treatment as measured over 3-months. Secondary Aim 1 for this study is retention on buprenorphine treatment over 12-months. This will be operationalized as time to first episode of buprenorphine treatment non-adherence. Non-adherence, or discontinuation of treatment, will be defined as a consecutive period of 7 or more calendar days without taking buprenorphine. Buprenorphine retention will be collected in a variety of ways for this study:

- (1) as part of the TLFB assessment, which will be administered at the baseline enrollment assessment and the 1-, 3-, 6-, 9-, 12-month follow-ups in which the participant will be asked to recall on which days they took their buprenorphine medications;
- (2) as part of weekly surveys completed during the study;
- (3) through medical record reviews at the treatment sites (as applicable when participants and clinics have provided proper releases of information) to review urine toxicology screens and/or prescription fill records;
- (4) through urine analysis at 1-, 3-, 6-, 9-, and 12-month follow-up

Medical Records will be reviewed, when applicable, for the following piece of information regarding buprenorphine treatment: (1) number treatment appointments scheduled with the buprenorphine provider, (2) number of treatment appointments completed with the buprenorphine provider, (3) number of treatment appointments scheduled but not completed by the participants with the buprenorphine provider, (4) urine toxicology results obtained as part of buprenorphine treatment only, (5) prescription fills for buprenorphine prescriptions through the VA pharmacy. The research team has extensive experience obtaining prescription fills and other data through CPRS from prior studies.

